#### Social support measures:

Diabetes-related supportive and obstructive family behaviors are measured by patient report on the Diabetes Family Behavior checklist. Family behaviors: supportive and non-supportive sub-scores of the Diabetes Family Behavior Checklist: supportive ranges from 4-45, non-supportive ranges from 7-35.

Diabetes-specific social support is measured by the Diabetes Care Profile Support Questions, with sub-scores for perceived disease specific support needs and perceived disease specific support received. Diabetes Care Profile support questions: Support wanted, and support received. Each range from 5 to 30, high scores indicating high desire for support and higher support received.

General social support is captured by the Norbeck Social Support Questionnaire Emotional and Tangible subscales. General social support: Norbeck Social Support Questionnaire, emotional sub score (ranges 0-16, with higher scores indicating higher perceived emotional support) and tangible sub score (0-8, higher score indicating higher perceived tangible support). While the

sub scores are highly correlated, the authors do not recommend Cronbach's alpha as a test of internal validity. However the Pearson correlations between the emotional support items was 0.96 and the tangible support items was 0.89.

(<http://eileengigliotti.com/uploads/1/1/0/2/110241155/nssq-psychometric.pdf>)

Supporter diabetes-related distress is measured by response to the Partner Distress Scale, which was initially developed for partners of patients with type 1 diabetes, but is used in this expanded support context with permission of the scale author. The self-report scale consists of 21 items in four domains: "my partner's diabetes management", "how best to help", "diabetes and me", and "hypoglycemia". The Cronbach's alpha was 0.76. It has not been previously validated in Spanish speaking population. For this study, the scale was translated and back translated by separate 2-person native Spanish speaking teams. Greater partner distress is correlated with higher A1C among patients and worse self-care, as is lower satisfaction with relationship with the partner

Report of frequency of patient-supporter contact and proportion of communication that is about diabetes is collected from the patients and confirmed by collecting this information from the supporter as well.

Potential modifiers at baseline

Mobile technology use: Mobile technology use will be measured by questions modeled after the Pew Hispanic Center survey with the addition of questions about frequency of contact between the patient and supporter, and the proportion of communication that is about diabetes. Supporter mobile usage is also captured with the Pew questions.

Health literacy: Health literacy is measured by the Brief Health Literacy Screen developed by Chew, et al. This screen has been validated in English and Spanish speakers.

Age: collected from medical records

Ethnicity: Collected by patient self-report, with option for decline to state

Race: collected by patient self-report, with option for more than one race and decline to state

## **Statistical Analysis**

### Primary and Secondary Outcomes

The primary outcome in this trial is the change in A1C from baseline to six-months, with a priority secondary outcomes of change in A1C from six to twelve months, with the exposure of interest of TExT-MED+FANS.

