### **Study Objectives:**

#### Primary Objective:

1. Examine the change in percent glycosylated hemoglobin at 6 months for FANS supported patients vs non-augmented support patients.

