#### Secondary Objectives:

1. Examine the change in percent glycosylated hemoglobin at 12 months for FANS supported patients vs non-augmented support patients.
2. Examine changes in psychosocial and behavioral outcomes at 6 and 12 months for FANS supported patients vs non-augmented support patients.

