## **Hypothesis Analysis**

Initial changes in outcomes (primary and secondary) will be compared between groups with paired t-tests. This will be followed by a longitudinal method with a mixed effects regression model to account for correlated outcome data (zero-six month and six-twelve month changes) and loss to follow up. Analyses will be conducted by intent-to-treat, with participants analyzed according to their randomized intervention regardless of adherence.

Because change in A1C is the outcome, participants who drop out prior to six-months will not be included in the analysis. All participants who complete the twelve-month study will provide two outcome measures of six-month change: a zero-six month measure of treatment efficacy, and a six-twelve month measure of sustainability of treatment effect. The linear mixed effects model will include a random intercept term for participants. Fixed effects will include treatment allocation, initial level of A1C (zero month measure for treatment efficacy, six-month measure for sustainability), and a covariate of study period (zero-six month, six-twelve month). The main effect of treatment will test for group differences over both zero-six and six-twelve month periods. An interaction term of treatment by study period will test for differences in treatment effects by study period; treatment effects will be estimated and tested for differences by study period in this interaction model. Model assumptions including normality of model residuals and homogeneity of variance will be evaluated. A sensitivity analysis confined to adherent participants (those who have not opted out of messages and have received 75% or greater of messages confirmed by message delivery platform) will be conducted. Mixed effects linear regression models will be conducted on secondary outcomes as detailed above.

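### Secondary objective 1 asks for the A1C change at 12 months, but the SAP prespecifies no month-12 comparison of the arms

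*SAP*

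**What the plan says.** The SAP's primary objective is: "Examine the change in percent glycosylated hemoglobin at 6 months for FANS supported patients vs non-augmented support patients". Secondary objective 1 repeats the sentence with a later time point: "Examine the change in percent glycosylated hemoglobin at 12 months for FANS supported patients vs non-augmented support patients". Secondary objective 2 covers both visits in one phrase: "Examine changes in psychosocial and behavioral outcomes at 6 and 12 months for FANS supported patients vs non-augmented support patients".

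The section Primary and Secondary Outcomes defines the primary outcome as the A1C change from baseline to six months. It then lists "priority secondary outcomes of change in A1C from six to twelve months".

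Under Hypothesis Analysis, each participant who completes the study supplies two outcomes: "a zero-six month measure of treatment efficacy, and a six-twelve month measure of sustainability of treatment effect". Changes "will be compared between groups with paired t-tests" as a first step. A mixed model with a random intercept follows, with treatment, study period and starting A1C as fixed effects, the last described as "initial level of A1C (zero month measure for treatment efficacy, six-month measure for sustainability"). On the treatment term the SAP says: "The main effect of treatment will test for group differences over both zero-six and six-twelve month periods". A treatment-by-period interaction then gives an effect for each period. The same approach is carried over to the other secondary outcomes.

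**The concern.** Secondary objective 1 gives no start point for the 12-month change. Baseline is the natural reading, for two reasons. The primary objective uses the same words, and its change is defined from baseline. Objective 2 also places the 6- and 12-month changes under one phrase, which suggests one common start.

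On that reading the SAP names no result that answers objective 1. What it does name answers a different question: what happened between months 6 and 12, after the text messages stopped (Protocol 2.4.4). If that result is taken as the answer to objective 1, a benefit still fully present at month 12 looks smaller than it is. A benefit that has disappeared looks like harm, while the main effect over both periods still looks like benefit. With planned contrasts that can differ in sign and no named one, the month-12 answer would have to be picked after the results are known.

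**Working it through.** The documents give no figure to reproduce, so the check is algebra followed by an illustration.

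**Definitions.** D6 and D12 are the arm differences in mean A1C (FANS minus control, negative favours FANS) at months 6 and 12. The baseline difference is zero in expectation by randomisation. In the planned interaction model, t1 and t2 are the treatment effects in periods 0-6 and 6-12, and b is the common slope on period-starting A1C.

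**What each planned contrast estimates**

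- Raw 6-12 comparison: D12 - D6. This assumes that a two-sample comparison is meant, because the SAP compares groups although it calls the test paired.
- Period 1: D6 = t1 + b×0, so t1 = D6. The primary contrast is intact.
- Period 2: D12 - D6 = t2 + b×D6, so t2 = D12 - (1+b)×D6.
- Main effect: an average over the two periods, roughly (t1 + t2)/2.

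The period-2 effect equals D12 only if D6 = 0 or b = -1. Rearranged, D12 = t2 + (1+b)×t1. The model therefore contains the answer, but the SAP does not specify this combination.

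**By hand.** Assume D6 = -0.8 and b = -0.5 (correlation 0.5, equal SDs, no truncation).

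- Benefit fully kept, D12 = -0.8: t2 = -0.8 + 0.5×0.8 = -0.40. The raw 6-12 contrast is 0.
- Benefit fully lost, D12 = 0: t2 = 0 + 0.5×0.8 = +0.40. The raw 6-12 contrast is +0.8, and the main effect is about (-0.80 + 0.40)/2 = -0.20.

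**By simulation, with the entry limit.** Only the 8.5 limit comes from the SAP (Table 1). Assumed: baseline truncated at 8.5 from a normal with mean 8.0 or 9.5; SD 1.5 to 2.5; exchangeable or first-order autoregressive correlation; no dropout; 600,000 per arm. The slope b lay between -0.74 and -0.30, and t1 was about -0.80 throughout.

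| True state at month 12 | D12 | Contrast | Correlation 0.5 | Correlation 0.3 to 0.7 |
|---|---|---|---|---|
| Benefit kept | -0.8 | Period 2 | -0.47 to -0.40 | -0.59 to -0.24 |
| Benefit lost | 0 | Period 2 | +0.33 to +0.41 | +0.21 to +0.56 |
| Benefit lost | 0 | Main effect | -0.25 to -0.20 | -0.31 to -0.12 |

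The period-2 values scale with D6. A fully kept benefit gives t2 = -b×D6, which is 30% to 74% of its true size. A baseline-adjusted month-12 contrast and the derived t2 + (1+b)×t1 were both within 0.01 of D12 in every setting.

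**Interval coverage.** Assumed: 75 per arm, mean 9.5, SD 2, D6 = -0.8, 4,000 trials per setting.

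- The period-2 95% CI contains D12 in about 89%, 75% and 42% of trials at correlations 0.3, 0.5 and 0.7, against 95% for a direct month-12 contrast.
- At correlation 0.5 the figure is 90% if D6 = -0.4 and 53% if D6 = -1.2. With 50 or 100 per arm at D6 = -0.8 it is about 82% or 68%.
- When the benefit is lost, the period-2 effect significantly favours control in 10%, 25% and 58% of trials (correlations 0.3, 0.5, 0.7), against 2-3% for the month-12 contrast.
- The derived combination had 95-97% coverage, with a standard error 3% to 17% larger than the direct contrast.

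**Late effect.** If D6 = 0 and D12 = -0.5, the raw and adjusted 6-12 effects are both -0.50, as the algebra predicts. The mismatch arises only when there is an effect at month 6.

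**The case against.** The strongest reply is that the objective's start point is undefined and the working sections agree with each other: the outcome variable is a six-month change throughout, and the 6-12 change is explicitly labelled sustainability. On that reading objective 1 has its outcome and its estimate, and only the wording of the objective needs attention. This reading is possible. It still requires the objective and the outcome to be reconciled.

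A second reply is that nothing is lost, because the 0-6 and 6-12 changes of a completer sum to the 0-12 change and the model yields D12. That is correct. But the adjusted effects do not simply add: the combination needs b, and its CI needs the covariances. The SAP calls for neither.

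Third, the interaction model reports both period effects, so a reversal would be visible and the main effect would not be read alone. This reduces the risk of a misleading main effect. It does not say whether the arms differ at month 12. It is also fair that a positive 6-12 effect after a lost benefit is the correct direction for a sustainability measure, and that the coverage figures score the interval against a quantity the SAP does not claim it estimates.

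Fourth, the numerical sizes are all assumed, and extending the fix to objective 2 adds many comparisons. Both points stand. The conclusion rests on the algebra; the figures only illustrate it. The patient-reported scales in the SAP give about 18 scores (6 self-care, 6 single scales, 6 support sub-scores), so multiplicity needs a sentence.

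**Conclusion.** The concern holds and should be fixed. As written, the SAP prespecifies no contrast that estimates the arm difference in A1C at month 12, and its nearest candidates can give the wrong size or the wrong sign for it. This follows from the model itself whenever there is an effect at month 6 and b is not -1. How far off the results would be depends on D6, the between-visit correlation and the sample size, none of which the documents give.

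The conclusion assumes that the 12-month change is measured from baseline. If the sponsor meant the 6-12 change, the defect is confined to the wording of the objective. The 6-12 analysis is valid for sustainability, and the primary 0-6 comparison is not affected.

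**What to change.** In Primary and Secondary Outcomes and in Hypothesis Analysis, name a baseline-adjusted month-12 arm difference in A1C, with 95% CI, as the analysis of secondary objective 1. One way is to model month-6 and month-12 A1C on baseline A1C, treatment, visit and treatment by visit, and take the month-12 contrast. The combination t2 + (1+b)×t1 from the planned model also works, with a somewhat larger standard error.

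Keep the 6-12 change as the stated sustainability analysis, reported beside the new contrast. State that neither it nor the main effect over both periods is the test of objective 1. Add the same month-12 contrast for the 12-month outcomes in objective 2, and say how multiplicity among them is handled.

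The Planned Subgroup Analysis section shows that this SAP text was written after enrollment ended. The addition should therefore be dated, with a statement of whether outcome data had been seen by arm.

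If the 6-12 change was intended, reword secondary objective 1 to say so.

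The cost is SAP wording and one extra contrast for A1C, plus one for each 12-month outcome under objective 2. No planned analysis is removed. For A1C no new data are needed: Protocol 2.3.2 lists it among the physical measurements, and Table 2.3.2 schedules these at enrollment, 6 and 12 months. The alternative costs one reworded sentence.

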### **Preliminary Analysis**

Normality of the outcome variable (six-month change) will be graphically evaluated.

## **Hypothesis Analysis**

Initial changes in outcomes (primary and secondary) will be compared between groups with paired t-tests. This will be followed by a longitudinal method with a mixed effects regression model to account for correlated outcome data (zero-six month and six-twelve month changes) and loss to follow up. Analyses will be conducted by intent-to-treat, with participants analyzed according to their randomized intervention regardless of adherence.

Because change in A1C is the outcome, participants who drop out prior to six-months will not be included in the analysis. All participants who complete the twelve-month study will provide two outcome measures of six-month change: a zero-six month measure of treatment efficacy, and a six-twelve month measure of sustainability of treatment effect. The linear mixed effects model will include a random intercept term for participants. Fixed effects will include treatment allocation, initial level of A1C (zero month measure for treatment efficacy, six-month measure for sustainability), and a covariate of study period (zero-six month, six-twelve month). The main effect of treatment will test for group differences over both zero-six and six-twelve month periods. An interaction term of treatment by study period will test for differences in treatment effects by study period; treatment effects will be estimated and tested for differences by study period in this interaction model. Model assumptions including normality of model residuals and homogeneity of variance will be evaluated. A sensitivity analysis confined to adherent participants (those who have not opted out of messages and have received 75% or greater of messages confirmed by message delivery platform) will be conducted. Mixed effects linear regression models will be conducted on secondary outcomes as detailed above.

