2.6 RANDOMIZATION

Envelopes are located in the Research Lab Room drawer. All envelopes are accounted for and under no circumstances should be tampered with. This process is **ONLY** to be completed at the time Supporter verbally consents and agrees to participate in study. All envelopes are in order and thus need be used sequentially.

Once Supporter verbally consents to participate, grab a sealed unused envelope. Randomization will occur after Supporter completes enrollment survey and study requirements. Randomization Form in RedCaps will need to be completed delineating which arm was the Supporter assigned to.

Open envelopes will be placed with the enrollment package, to allow staff to determine participant's supporter was enrolled. Under no circumstances throw away envelop and its context.

[figure not shown]

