### **Study Design:**

In this twelve-month, comparative effectiveness randomized controlled trial (enrollment period July 2017 to October 2018), ED patients with poorly-controlled diabetes mellitus from an urban,

safety net medical center were randomized to one of two arms: [1] an mHealth intervention for self-management education augmented by mHealth augmented social support (TEXT-MED+FANS) or [2] the same patient-oriented mHealth intervention with minimally augmented social support (TEXT-MED + pamphlet).

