#### Enrollment & Randomization

The goal of this investigation is to study augmenting existing social support via mHealth, so patients were only eligible to be enrolled in the study if a supporter agreed to participate as well; however, this took up to three weeks to contact and enroll the supporter. Given the potential lag, all potentially eligible patients were registered in the SHERPA platform used by Agile Health while in the ED. Occasionally, patients lacked cellular service in the ED and were not able to text-in the Federal Communications Commission-required YES message to opt in during their initial ED visit; we texted and called these patients daily for up to one week until they texted back in YES. The supporter was not contacted until after the patient was fully registered in the system. If a supporter was not eventually enrolled as well, the patient still received the patient text-messaging program, however they were removed from further participation in the study.

Supporters were enrolled either in the ED during the initial contact with the patient or remotely by telephone if they were not present in the ED. Each patient was instructed to rank up to three family or friends who would provide them the most support. As the intervention encourages communication between a patient and a supporter, only one supporter was enrolled per patient to not overwhelm patients with suggestions for healthy living from multiple loved ones. We collected multiple contact numbers for each potential supporter from each patient. We called daily for up to three weeks to enroll supporters.

Enrolling supporters consisted of verbal consent, confirming age>18 and the ability to send and receive text messages, completion of supporter survey instruments and registration in the

SHERPA platform. Registration in the SHERPA system required a YES text back from the supporter. If the supporter did not respond with the required text-in YES message, we called them daily to remind and assist them with completing registration. After supporter enrollment was completed, the dyads were randomized to the FANS mHealth-augmented social support or pamphlet-based social support education for the supporter. All patients received the TExT-MED patient program.

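### The SAP's first between-arm test is a paired t-test, but the two arms are independent and no pairs exist to run it on

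*SAP*

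**What the plan says.** The SAP's Primary Objective is to "Examine the change in percent glycosylated hemoglobin at 6 months for FANS supported patients vs non-augmented support patients". Primary and Secondary Outcomes defines the endpoint as a within-patient change: "The primary outcome in this trial is the change in A1C from baseline to six-months".

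Hypothesis Analysis then opens with the test at issue: "Initial changes in outcomes (primary and secondary) will be compared between groups with paired t-tests". A linear mixed model follows, with a random intercept for participants and fixed effects for treatment, initial A1C and study period. A treatment-by-period interaction is added, and "treatment effects will be estimated and tested for differences by study period in this interaction model". The same section claims intention-to-treat analysis, yet "participants who drop out prior to six-months will not be included in the analysis".

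On design, Study Design says that patients from an urban "safety net medical center were randomized to one of two arms". Under Enrollment & Randomization, once the supporter is enrolled, "the dyads were randomized to the FANS mHealth-augmented social support or pamphlet-based social support education for the supporter". Protocol section 2.6 describes sealed envelopes: "All envelopes are in order and thus need be used sequentially".

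**The concern.** A paired t-test analyses the differences within defined pairs. Used between groups, it needs each FANS patient to be linked to a particular pamphlet patient by matching, crossover or something similar. The plan sets up no such link.

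This is the first comparison named for the primary outcome and for every secondary outcome. An analyst holding to it would have to substitute another test, choose an order in which to line up unrelated records, or drop patients until the arms are equal. Dropping patients who completed follow-up would contradict the SAP's intention-to-treat statement. Nothing in the SAP says whether the t-test or the mixed model is confirmatory, so a result from the faulty test could be reported as the answer to the primary objective.

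**Working it through.** The plan gives no sample size, SD, effect size or dropout rate, so it has no figure to reproduce. The design text settles whether the test applies. The arithmetic only sizes the consequence, and every numerical input is an assumption.

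**1. Is there any pairing that would make the sentence work?**
- *Patient with supporter.* Both members of a dyad are in the same arm, and only the patient has an A1C outcome. This gives no between-arm pair.
- *Baseline with six months.* This pairing is already used up in the change score.
- *Patient in one arm with patient in the other.* No matching is described. Envelopes are taken in sequence, and the mixed model has no pair term.
- *Separate pre/post tests within each arm.* The sentence says between groups, and such tests do not compare arms. With the same true change of −0.5 in both arms and SD of change 2.0, each arm is significant with simulated probability q = 0.270, 0.397 and 0.685 at 30, 50 and 100 per arm. By 2q(1 − q), one arm is significant and the other not in about 0.39, 0.48 and 0.43 of trials; direct simulation gave 0.39, 0.47 and 0.44. The independent t-test rejected in 5% to 6%. The discordance shrinks when the common change is large: at −1.5 it is 4% at 30 per arm and nearly nil at 100.

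**2. Could the test be computed?** Assume n randomised per arm and independent dropout d before six months. Completers per arm are then Binomial(n, 1 − d), and

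P(arms differ) = 1 − Σₖ [Bin(k; n, 1 − d)]²

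| n per arm | d | P(arms differ) | Mean number discarded to equalise |
|---|---|---|---|
| 30 | 0.1 | 0.826 | 1.8 |
| 75 | 0.2 | 0.919 | 3.9 |
| 100 | 0.3 | 0.938 | 5.2 |

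Run on 50 against 47 records, a standard paired-test routine returns an error.

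**3. If the arms happen to be equal, how much does record order matter?** With equal sample SDs, lining up the records in some order gives a chance correlation r, and

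t_paired = t_ind / √(1 − r), on n − 1 df

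Over random orders the 95% range of r is about ±1.96/√(n − 1). Start where the independent test gives exactly p = 0.05:
- n = 30: t_ind = 2.002 (58 df) and r = ±0.364. Paired t is 2.510 or 1.714 on 29 df, so p runs from 0.018 to 0.097.
- n = 75: t_ind = 1.976 (148 df) and r = ±0.228. Paired t is 2.249 or 1.783 on 74 df, so p runs from 0.027 to 0.079.

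**4. Error rate and verdicts in one fixed arbitrary order.** Simulation used 20,000 trials per setting, baseline A1C normal with mean 9.5 and SD 2.0 truncated at 8.5, visit correlation 0.3 to 0.7, and 30 to 100 per arm. Null rejection was between 0.046 and 0.054 for both the paired and the Welch test. The two verdicts differed in about 1% to 2% of null trials and, with a true effect, mostly in 1% to 6%, less where power is near 1.

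**5. Does the mixed model share the fault?** It treats allocation as a between-participant fixed effect and uses no pairs. In simulation (75 per arm, SD 2, adjacent-visit correlation 0.5, true effect −1.0 at six months and maintained at twelve), the zero-six month effect from the interaction model averaged −0.97 to −1.01 across separate checks. The treatment main effect pooled over both periods averaged about −0.76 to −0.77, so it does not answer the six-month question.

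**The case against.** The strongest reply is that this is a drafting slip. The outcome is already a change score, so the authors probably meant an unpaired t-test on changes, or else pre/post tests within arms. Nobody proposes pairing strangers in record order. The impossibility is visible from the design, so the wording can be corrected before any outcome is examined. An error message forces a correction and does not yield a wrong answer. Type I error is sound, and a single fixed order seldom changes the verdict. The SAP calls the t-tests initial, and the moderator analyses build on the mixed model, which suggests that the model was meant to carry the inference.

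Much of this stands, and it limits the weight of the point. The p-value ranges apply only at the margin of significance in equal-sized arms, a case with probability 0.06 to 0.17 under the assumptions above. Discarding patients is something an analyst might do, not something the plan prescribes.

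It does not remove the point. The two likely intentions lead to different analyses, one of which does not compare the arms, and a reader cannot tell which was meant. The SAP also never labels either analysis as primary. A slip in the first named hypothesis test still has to be corrected in the plan, before outcomes are examined.

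**Conclusion.** The concern holds. A paired t-test between these two arms has no defined pairs, and no reading of the sentence turns it into a valid between-arm paired comparison. That conclusion rests on the design text alone.

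The practical size is moderate. Under the assumed arm sizes and dropout rates, the test most probably could not be run. Where it could, the result would be arbitrary near the significance threshold but not biased towards false positives. The mixed model's zero-six month treatment effect does not depend on pairing and is a usable baseline-adjusted estimate. The check of it covered no dropout, so that reassurance is subject to the SAP's restriction to patients with six-month data. This should be fixed, but it does not undermine the trial's main model.

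**What to change.** Replace the paired t-test sentence in the SAP's Hypothesis Analysis with wording such as:

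> For continuous outcomes, zero-six month changes will be compared between randomised arms with independent two-sample (Welch) t-tests on the change scores, reported with the mean difference and 95% CI, as an unadjusted supporting analysis. The primary between-arm comparison is the baseline-adjusted zero-six month treatment effect from the treatment-by-period mixed model.

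A pooled-variance t-test would also cure the pairing fault; Welch avoids assuming equal variances. If within-arm pre/post tests were also intended, list them separately as descriptive and state that they are not a comparison of arms. The second sentence should name the zero-six month effect explicitly, because the pooled main effect answers a different question.

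The cost is two sentences of SAP text, with no new data and no extra patients.

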### **Study Limitations:**

There are several limitations in this study:

1. Assessing “dose” of messaging may be difficult, as per current report from Agile Health, there have been no messages bounced back. They believe this is due to the lower tier cell phone providers used by some participants, which do not accurately report incoming and dropped messages.
2. Healthy behaviors are measured by self-report.
3. We did not include a social desirability measure in baseline data, so assessing for potential social desirability bias in responses would be difficult.
4. The setting of this study is very specific and limits generalizability to larger populations.

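### The primary A1C analysis leaves out randomised patients lost before month 6, and nothing in the SAP covers or tests that loss

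*SAP*

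**What the plan says.** The primary outcome is the change in A1C from baseline to month 6 (SAP, Primary and Secondary Outcomes). The Hypothesis Analysis section then makes these statements:

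- **Principle.** "Analyses will be conducted by intent-to-treat, with participants analyzed according to their randomized intervention regardless of adherence".
- **Model.** A mixed model with a random intercept per participant is used "to account for correlated outcome data (zero-six month and six-twelve month changes) and loss to follow up".
- **Outcome rows.** "All participants who complete the twelve-month study will provide two outcome measures of six-month change": one for months 0-6 and one for months 6-12.
- **Covariate.** The fixed effects include the "initial level of A1C (zero month measure for treatment efficacy, six-month measure for sustainability").
- **Exclusion.** "Because change in A1C is the outcome, participants who drop out prior to six-months will not be included in the analysis".
- **Sensitivity.** The only one planned is described as "A sensitivity analysis confined to adherent participants", meaning patients who did not opt out and received at least 75% of messages.

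The SAP contains no missing-data assumption, imputation, comparison of dropout by arm or tipping-point analysis. The Study Limitations section opens with "There are several limitations in this study" and lists four; attrition is not one of them. Separately, a secondary objective is to "Examine the change in percent glycosylated hemoglobin at 12 months for FANS supported patients vs non-augmented support patients", while the modelled later outcome is the change from month 6 to month 12.

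**The concern.** A reader of the Hypothesis Analysis section would take it that the mixed model deals with dropout. For the primary outcome it cannot, because a patient with no month-6 A1C contributes nothing to it. Analysis by assigned arm regardless of adherence is kept, and the exclusion is openly stated. What is lost is the inclusion of all randomised patients, and the claimed handling of loss for the outcome that matters most.

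If patients are lost for reasons tied to their unseen month-6 A1C, and this differs between arms, the estimated effect can be too large or too small. No planned analysis would show it. The adherent-only analysis narrows the population further and says nothing about the missing outcomes.

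There is also no rule for a patient who misses month 6 but attends month 12. The SAP assumes that every 12-month completer has two changes, so such a patient's month-12 value would go unused. The documents do not say whether any such patient exists.

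**Working it through.** The documents give no sample size, SD, effect size, dropout rate or alpha, so there is no planned figure to reproduce. Step 1 rests on the documents alone. Steps 2 and 4 to 6 use assumed inputs and are illustrations.

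**1. Who contributes to the stated model.** After enrolment, in-person measurement visits fall only at months 6 and 12 (Protocol Table 2.3.2), so no A1C is scheduled between baseline and month 6.

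| A1C seen at month 6 | A1C seen at month 12 | 0-6 row | 6-12 row |
|---|---|---|---|
| yes | yes | yes | yes |
| yes | no | yes | no |
| no | yes | no | no |
| no | no | no | no |

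Month-6 A1C is the end value of the first change and both the start value and the covariate of the second. Without it there is no row at all.

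**2. Does the mixed model recover anything?** The stated model (random intercept, treatment by period, initial A1C) was simulated in 12 runs of 4,000 patients, with an assumed true effect of -0.40 and about 25% missing month 6.

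| Loss before month 6 depends on | Full data | Completers | Stated mixed model |
|---|---|---|---|
| baseline A1C only | -0.378 | -0.378 | -0.377 |
| the unseen change, one arm only | -0.395 | -0.643 | -0.646 |

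In the first case there is no bias. In the second the mixed model simply repeats the completer estimate.

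**3. Size of the bias.** Let p be the fraction missing month 6 and g the baseline-adjusted gap in A1C (unseen minus seen), for control (C) and FANS (F). Each arm's mean is its seen mean plus p x g, so

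completer estimate - true effect = pC x gC - pF x gF.

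Equal p and equal g give zero. Unequal p or unequal g gives bias in either direction.

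**4. Illustration.** Assumed: month-0 and month-6 A1C with SD 2 and correlation 0.5, true effect -0.80, and log-odds of missing month 6 linear in standardised month-6 A1C. The estimator is least squares of month-6 A1C on arm and baseline in completers, with 2,000,000 simulated patients per arm.

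| Log-odds slope per SD, FANS / control | Missing, FANS / control | Completer estimate |
|---|---|---|
| 1 / 1 | 25% / 25% | -0.80 |
| 0.25 / 0.5 | 25% / 25% | -0.71 |
| 0.5 / 1 | 25% / 25% | -0.65 |
| 1 / 0.5 | 25% / 25% | -0.94 |
| 0.5 / 0.5 | 20% / 30% | -0.73 |
| 1 / 1 | 20% / 30% | -0.68 |
| 1 / 1 | 30% / 20% | -0.92 |
| 0 / 1 (extreme) | 25% / 25% | -0.48 (-0.60 at 15%, -0.35 at 35%) |
| 1 / 0 (extreme) | 25% / 25% | -1.12 (-1.00 at 15%, -1.25 at 35%) |

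In the extreme rows g is about 1.3, so p x g is about 0.32, which agrees with step 3.

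**5. How far missing values must shift to change a conclusion.** Assumed: 75 per arm, 25% missing (56.25 seen per arm), two-sided 5%, SE held fixed.

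- SE = sqrt(2 x 4 x 0.75 / 56.25) = 0.327. The critical difference is 1.98 x 0.327 = 0.647.
- An estimate of -0.80 loses significance when missing FANS values are shifted by (0.80 - 0.647) / 0.25 = +0.61 A1C points. The shift is +1.29 at 15% missing and +0.30 at 35%. At 25% missing it is about 0 with 50 per arm and about +1.0 with 100.
- A non-significant -0.40 becomes significant at (0.40 - 0.647) / 0.25 = -0.99, with a range of -1.4 (15% missing) to -0.85 (35%).
- Shifting both arms by +1 leaves the estimate at -0.80, so a common shift tests nothing.

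**6. What a model of A1C level would gain.** Assumed: 75 per arm, 85% retained from month 6 to 12. At 25% missing month 6, the month-12 SE falls from 0.351 to 0.322 (8%) if half of those patients return, and not at all if none do. The gain runs from 2% (15% missing, a quarter return) to 17% (35% missing, three quarters return). At month 6 it is at most 1.5%.

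**The case against.** The strongest reply is that the SAP hides nothing. It defines intent-to-treat by allocation regardless of adherence, and it states the exclusion and its reason. A mixed model does help with loss between months 6 and 12, so the loss-to-follow-up wording is too broad rather than false. All of that stands, which is why the point concerns a missing assumption and a missing sensitivity analysis, not a breach of allocation.

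A baseline-adjusted completer estimate is also valid if loss depends only on arm and baseline A1C. That is true, but the SAP neither states this condition nor examines it.

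There is no evidence of differential loss. The protocol requires stable contact (section 2.3.1) and re-verifies patient contact details at each visit (Table 2.3.2). Month-6 payments do not differ by arm: $50 for patients and $25 for supporters. The intervention-only payments, a $100 exit interview for patients (section 2.3.2) and $100 for supporters (Table 2.5), fall at month 12 and bear mainly on later loss. This also stands. It is a reason to report loss by arm, not a sign of bias.

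The numbers rest on assumed inputs. The one-arm cases are extremes, and the tipping values depend heavily on the assumed sample size. They show that the issue can matter, not that it does.

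Finally, a model of A1C level does little for month 6 and does not repair informative loss. Its case rests on month 12 and on the 12-month objective.

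**Conclusion.** The concern holds. The primary A1C result is a month-6 completer analysis, the stated handling of loss to follow-up does not reach it, and no analysis of missing outcomes is planned. These three statements follow from the SAP text and need no assumed numbers.

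The size and direction of any bias are unknown. It is zero if the missing fraction and the gap between unseen and seen A1C are the same in both arms. Under the illustrative inputs, a true -0.80 is estimated between -0.65 and -0.94 in the milder unequal scenarios, and as -0.48 or -1.12 in the one-arm extremes at 25% missing. The plan should be changed because the condition under which its result is valid is unstated and untested. It has not been shown that the result would be wrong.

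**What to change.** 1. Replace the exclusion sentence. Include all randomised patients, state the assumption (missing at random given arm and observed A1C), and report the number missing at each visit by arm.
2. Add one delta-adjusted analysis for missing month-6 A1C. Impute under that assumption, then shift the imputed values separately by arm and in both directions until the conclusion (confidence interval or test, at a stated alpha) changes.
3. Model A1C level at months 0, 6 and 12 with a common baseline mean, unstructured covariance and arm-by-visit contrasts at months 6 and 12. This uses every observed value, including month-12 values from patients who missed month 6, and answers the 12-month objective directly.
4. Keep the 6-12 month change as a separate sustainability analysis, and label the month-6 completer analysis as such.

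If the change-score model stays primary, limit the loss-to-follow-up statement to loss between months 6 and 12 and still carry out step 2.

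The cost is SAP wording and modest programming, with no new data. The drawbacks are reliance on missing at random, which step 2 tests, and almost no gain in precision for the primary outcome.
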